**The following documents are currently attached to this item:**

*There are no documents attached for this item.*

**Subject compensation\***

Will subjects be financially compensated for their participation?

Yes

**The following documents are currently attached to this item:**

*There are no documents attached for this item.*

**If there is subject compensation, provide the schedule for compensation per study visit or session and total amount for entire participation, either as text or separate document**

Subject compensation will vary by study group. MDD participants will receive \$75.00 for the 1st MRI, \$100.00 for the 2nd MRI, and \$125.00 for the 3rd MRI, if applicable. MDD subjects have the potential to receive an additional \$50.00 bonus for completing all of the Good Days Ahead homework for CCBT and 85% of the remote monitoring (e.g., Beiwe self-reports) and Good Days Ahead adherence questions (e.g. Ethica self-reports). Therefore, MDD participants can receive up to \$225.00 to \$350.00 total. IF PARTICIPANTS IN THIS ARM ARE ALSO PARTICIPATING IN PROTOCOL 824132, THEY WILL NOT RECEIVE THE \$75.00 PAYMENT FOR THE INITIAL MRI SCAN; PARTICIPANTS WILL BE COMPENSATED FOR THIS SCAN THROUGH PROTOCOL 824132. THEREFORE, THE MAXIMUM COMPENSATION FROM THIS PROTOCOL, FOR DUAL PARTICIPANTS, WILL BE \$150 OR \$275.00. Subject payments for the patient participants increase incrementally for MRI visits to encourage study completion; the bonus of \$50.00 for CCBT exercise completion & remote self-reports is to encourage treatment compliance. These participants will additionally be receiving diagnostic assessments and treatment for their depression at no cost. Healthy Controls will receive \$20.00 for completing screening assessments and \$95.00 for the MRI scan. Participants will receive a bonus of \$15 for completing 85% of the remote self-reports on Beiwe. Therefore, healthy controls can receive a total of \$130.00 if study is completed. Since healthy controls do not have the potential to benefit from diagnostic assessments or treatment, they will receive the aforementioned compensation to encourage healthy individuals to participate. IF HEALTHY CONTROL PARTICIPANTS ARE ALSO PARTICIPATING IN PROTOCOL 824132, THEY WILL NOT RECEIVE THE \$95.00 PAYMENT FOR THE INITIAL MRI SCAN; PARTICIPANTS WILL BE COMPENSATED FOR THIS SCAN THROUGH PROTOCOL 824132. THEREFORE, THE MAXIMUM COMPENSATION FROM THIS PROTOCOL, FOR DUAL PARTICIPANTS, \$35. Participants will receive their human subjects payment at the end of their own study participation. Subjects will be compensated through University of Pennsylvania supported Greenphire ClinCard. This is a reloadable prepaid card (similar to a debit/credit card) which allows funds to be available immediately. Study staff will provide participants with a ClinCard Cardholder FAQ: US document (attached). Subjects who do not feel comfortable with the Greenphire ClinCard may be compensated by a check, in lieu of the ClinCard. We are not stating this option in the ICF, as we would prefer all participants to use the ClinCard for consistency; however, we acknowledge that not all individuals will feel comfortable with this method and therefore, if a participant expresses discomfort, we will then verbally offer them the option of being paid with a check. If participants opt to have the payment provided to them in the form of a check; it will be mailed to their home address. Participants will be required to complete a C-2 and a W-9, including providing their full social security number, in order to receive the study payment.

# Study Procedures

## Suicidal Ideation and Behavior

Does this research qualify as a clinical investigation that will utilize a test article (ie- drug or biological) which may carry a potential for central nervous system (CNS) effect(s)?

No

## Procedures

Participants will complete a phone screen or a online self-report screener to determine eligibility. If the participant is eligible, they will be scheduled for an in-person screening visit. Information collected during the pre-screening will not be used in the data analysis; pre-screening information will be collected and retained in REDCap. Participants will be asked to authorize the release of the medical records for the purposes of determining their eligibility for this study. Individuals who are patients in the Penn system will be asked for verbal consent during the pre-screening to release their PennChart electronic medical record. Data from the PennChart electronic medical record will be viewed only. The information will not be downloaded or stored. Individuals who are not in the Penn system will be asked to complete an medical record release authorization form at the screening visit after their have signed the informed consent. Upon receipt of their medical records, personal health information and identitifiers will be redacted to mitigate the risk of lost of confidentiality and privacy. Visit 1 (Screening) - all participants will have the study described to them in detail, including the risks and study procedures as outlined in the informed consent form and will sign the ICF and HIPAA authorization, prior to any study procedures being completed. Participants will be screened for symptoms of psychological disorders and severity of major depressive symptoms by a trained research team member. If determined eligible, HEALTHY CONTROLS will be scheduled for return to complete a 1-hour fMRI scan and baseline visit, in which self-report measures, including reports of mood, behavior, and thoughts will be collected, as well as neuropsychological testing. Healthy controls will begin "Remote Monitoring" by being given an actigraph to wear 24 hours a day for 8 weeks and will have Beiwe installed on their cell phones. The mobile application has two elements: Passive data collection: Behavior data is gathered unobtrusively through a background process on the mobile device. The background process is launched automatically by the application once the user logs in. After the initial logon, the process continues to be automatically launched whenever it is not already running (on phone restart or other events that terminate the process). Active data collection: Surveys and other self-report data are gathered through user input. This is achieved in two ways: (i) the user receives a notification that a survey is available and upon launch the application and they are shown all the surveys available at that time. Controls will return for an in-person visit following the 8 weeks of remote monitoring to return actigraph, have Beiwe disabled from cell phone, and receive ClinCard compensation. If determined eligible at screening, MDD (EXPERIMENTAL GROUP) participants will begin CCBT treatment within 4 weeks after completing baseline assessments. Half of the depressed participants will begin 8 weeks of CCBT within 2 weeks from completing baseline assessments (Early CCBT), and the other half after 2 weeks from completing pre-treatment baseline assessments (Later CCBT). Participants are randomly assigned to either (1) Early CCBT or (2) Later CCBT based on the a number randomly generated by the computer. All MDD participants will receive 8 weeks of CCBT within 4 weeks from completing baseline assessments. Participation duration may vary depending on the scheduling availability of the therapists, participants, and also our facilities. All CCBT participants will be scheduled for return for Visit 2 to complete a 1-hour fMRI scan and baseline visit, in which self-report measures, including reports of mood, behavior, and thoughts will be collected, as well as neuropsychological testing. Participants will begin "Remote Monitoring" by being given an actigraph to wear 24 hours a day for 8 weeks and will have Beiwe installed on their cell phones (see above for details of Beiwe). MDD subjects who are scheduled to begin CCBT after 2 weeks (Later CCBT) will complete an additional fMRI scan when they return to begin treatment. For the Later CCBT participants, the 2nd MRI scan is at least 2 weeks and up to 4 weeks from the 1st pre-treatment MRI scan. MDD participants will also have Ethica installed on their cell phones at their and complete 1 question/day regarding Good Days Ahead adherence on Ethica for 8 weeks when they being CCBT treatment. Again, this will be dependent on when subjects begin CCBT. Ethica will be used for active data collection, which includes surveys and other self- report data are gathered through user input. This is achieved in two ways: (i) the user receives a notification that a survey is available and upon launching the application they are shown all the surveys available at that time. Participants will complete Good Days Ahead (GDA) computer training at their CCBT Week 1 visit. They will have CBT Clinical Contact with a licensed psychologist/psychiatrist at Weeks 1, 2, 4, 6, 8, & 9 of treatment. Additionally,

outcome measures will be assessed by an independent clinical evaluator (without knowledge of treatment assignment) at every in-person study visit. Weeks 3, 5 & 7 will be completed off-site (at home, preferably). Participants will have a final 1-hour fMRI scan at end of study during CCBT Week 9, in which self-report measures, including reports of mood, behavior, and thoughts will be collected, as well as neuropsychological testing. Both MDD and healthy control participants will complete a 15-minute computer task called "The Foraging Task" examining their responses to rewards during Visit 2. Foraging task Details: At the beginning of each trial, participants hold fixation on a central fixation square for 2.5 seconds. Afterwards the square turned green signaling they could make a choice. They needed to move the joystick to the nearby bush to earn a reward, displayed after a short period of time called handling time. On subsequent trials, participants could choose to go back to the same bush (stay). Reward however diminished for every subsequent attempt. At any point they could decide that the reward they are getting in that bush is not high enough and that they wanted to travel to a new non-depleted bush. If they wanted to leave and go to the next bush, they needed to move the joystick to the square on the other side of the screen, and then the bushes started sliding down as if they were traveling to the next bush. The amount of time it took to travel to the next bush depended on the environment. In one block it took 5s to travel to the next bush and in another it took 20s. There were unlimited number of bushes in the environment but they had a finite time in each one (6 min x 2 blocks). The remuneration would be based on the amount of berries they have collected by the end of the session. PLEASE SEE ATTACHED TABLES SHOWING SCHEDULE OF PROCEDURES FOR EACH STUDY GROUP. PARTICIPANTS WHO ARE ALSO PARTICIPATING IN THE 824132 PROTOCOL WILL PARTICIPATE IN BOTH STUDIES SIMULTANEOUSLY. VISITS 1&2 OF THE CURRENT PROTOCOL ARE MOSTLY ENCOMPASSED WITHIN THE FULL 824132 PROTOCOL, WITH THE EXCEPTION OF SOME SELF-REPORT MEASURES AND ANY CCBT PROCEDURES THAT WOULD OCCUR AT VISIT 2 FOR THE IMMEDIATE CCBT GROUP; THEREFORE THE DURATION OF THE FIRST 2 STUDY VISITS FOR DUAL PARTICIPANTS WILL BE SLIGHTLY LONGER THAN FOR THOSE WHO ONLY PARTICIPATE IN THIS CCBT PROTOCOL.

**The following documents are currently attached to this item:**

*There are no documents attached for this item.*

**Deception**

Does your project use deception?

No

**International Research**

Are you conducting research outside of the United States?

No

**Analysis Plan**

C.10. Statistical Analysis: Aim 1: Aim 1a: To assess whether there is a baseline difference in amygdala connectivity in MDD compared to the controls, we will use a two-stage data-driven approach. The first step will use multivariate distance- based matrix regression (MDMR) [85] to conduct a brain-wide test using the connectivity maps with the amygdala as the seed region (adjusted for in-scanner motion). This fully data-driven approach examines the functional connections between the amygdala and each region of the brain, and serves as an omnibus test of whether depression symptoms and treatment are associated with connectomic differences. We will then apply functional principal component regression (fPCR) to the amygdala-seeded correlation maps to assess patterns of baseline amygdala-connectivity that are associated with MDD adjusting for age and sex. fPCR extracts patterns that optimally explain variation in the baseline amygdala connectome across groups through eigenimages, and hence has more power than voxel-wise searches. These eigenimages indicate which regions contribute most to these patterns. The principal scores are generated by projecting each connectivity map onto the corresponding eigenimages, yielding a measure of the amount of signal for each subject that can be explained by a particular eigenimage. Guided by hypotheses generated based on the pilot observations, we will fit fPCR separately in the target networks CEN and DMN using the 7-network solution of Yeo et al. [86] and test the relationship between the principal scores in MDD compared to controls using logistic regression adjusting for motion, age, and sex. For eigenimages with scores differing between MDD and HC, the spatial pattern will be characterized using a structural (Harvard-Oxford) and functional (Craddock-200) atlas. We expect for fPCR to provide more sensitive and specific measurement of patterns of MDD-related amygdala- dysconnectivity in the CEN and DMN than regional averaging,

which we will also conduct for comparison. Aim 1b: To assess baseline differences between MDD and HC in Emotional Conflict task-induced activation in the dorsal ACC, DLPFC, and IFC, we will apply two approaches: First, perform the voxel-wise general linear model to detect group differences on the AHIF-AHIN contrast; Secondly, we will conduct brain-wide fPCR to explore variations that are associated with depression symptoms while controlling the anxiety symptoms. All analyses will be adjusted for age and sex, and corrected for multiple comparisons by controlling the false discovery rate. Aim 2: Aim 2a: To assess the effect of CCBT on the functional connectome, we will test for differences in amygdala-connectivity between MDD patients who receive treatment immediately (within 1-2 weeks of screening) and those who receive treatment later (within 3-4 weeks of screening). We will examine deficits identified in Aim 1 to compare the MDD groups treated immediately (1-2 weeks) vs. treated later (3-4 weeks) for changes in these regions, adjusting for motion, age and gender. We will also conduct a whole-brain feature search through structured functional principal component analysis (SFPCA) [87]. SFPCA incorporates the longitudinal design complexity and models variation in amygdala-connectivity induced by CCBT through dimension-reduced principal components that are associated with longitudinal changes. Instead of generating contrasts for each hypothesis, it utilizes all available data by explicitly modeling the correlation structures among the observed connectivity maps. Aim 2b: To assess changes of the conflict task-induced activity in ACC, DLPFC, and IFC, we will use the same techniques of SFPCA and targeted mixed-effects modeling adjusting for age and sex. We will also investigate the correlation between the patterns of treatment-induced connectivity and activation normalization. Further, we will investigate the dose-response relationship between total time engaged in CCBT and changes in brain connectivity and activity. Exploratory Aim: We will first use PCR to predict treatment response after CCBT using the baseline amygdala-connectivity map. To avoid overfitting, we will evaluate the prediction performance using bootstrapped cross-validation by iteratively applying learning predictive patterns to 90% of the subjects and testing on the remaining 10%. We will assess treatment response using continuous score changes in depression and anxiety, and remission status (defined by MADRS10 after CCBT). For continuous measures of response, we will assess predicted mean-square error (MSE) for symptomatic change in two ways: first, we will simply estimate the predictive performance of the principal scores. Next, we will compare a predictive model based on regression with only baseline depression scores to a model with both baseline scores and principal scores to assess the added value of the imaging markers. For remission status, we will assess both the predictive performance of the principal scores and the added value of these markers above baseline depression scores and other demographics (age, sex, socio-economic status) using receiver-operator characteristic (ROC) curve analysis. Differences in the performance will be assessed by building confidence intervals for increased area under the curve (AUC) using bootstrapped cross-validation. We will apply the same techniques to the contrast of parameter maps from the conflict task, as well as to the cortical thickness maps. We will build second stage meta-classifiers that integrate the patterns found using these functional and structural imaging measures using generalized linear modeling, which will allow us to integrate the imaging predictors with age, sex, and other demographic information. To assess the importance of baseline executive function measures, we will examine the improvement in predictive performance by including these into the meta-classifiers. Other machine learning algorithms such as support vector machines and random forests, as well as collaborative learning will also be explored to achieve optimal performance. We will also assess the amount of model improvement by incorporating joint resting-state, task-based activation, and cortical thickness patterns into the previous PCR model by calculating c-statistics and prediction indices (such as net reclassification improvement and integrated discrimination improvement etc.) sequentially. Finally, we will investigate sparse patterns of association between imaging measures and depression phenotypic measures using sparse canonical correlation analysis. \*\*\*NOTE REGARDING DATA ANALYSIS WITH PROTOCOL 826910\*\*\* Procedures and data elements are the same between #826910 and #832295, therefore they will not need to be reconciled. The data from the two study will be added together. Participant data from the Immediate CCBT group from #826910 and the early CCBT group from #832295 will be grouped together for analysis. Participant data from the Wait-list Followed by CCBT group from #826910 and the delayed CCBT group in #832295 will be grouped together for analysis.

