### ***Objectives***

#### **Overall objectives**

The overall objectives of the study are to examine novel potential neural circuit bio-markers of treatment response to computer-augmented cognitive behavioral therapy (CCBT) for people with MDD. Aim 1: Compare baseline resting state functional connectivity and task-induced activity between MDD and controls: Hypothesis 1a): Compared with controls, depressed participants will have disruptions in resting state functional connectivity in the amygdala-cognitive-executive (C-E) network and the amygdala-default mode network (DMN); and 1b) will have decreased emotional conflict task-induced activation in rostral/dorsal anterior cingulate cortex (ACC), dorsal lateral prefrontal cortex (DLPFC), and inferior frontal gyrus (IFG). Aim 2: Assess CCBT treatment effects on resting state functional connectivity and task induced activity in MDD comparing post-CCBT treatment to pre-CCBT treatment. Hypothesis 2a) Compared with pre-CCBT neuroimaging measures, following active treatment there will be increase in C-E connectivity and decreased amygdala-DMN connectivity. 2b) These changes will be correlated with symptom reduction and 2c) increases in rostral/dorsal ACC, DLPFC and IFG activation during the emotional conflict task. Exploratory Aim: 1a) Predict the effects of baseline brain measures on treatment outcomes. Hypothesis: Using clinical decision-support algorithms, clinical outcome trajectories and differential response to treatment will be predicted from baseline data (brain connectivity, task-based activity and cortical thickness). 1b) Predict the effects of baseline executive function on treatment outcomes. Hypothesis: Using clinical decision-support algorithms, clinical outcome trajectories and differential response to treatment will be predicted from baseline executive function data. Developing such algorithms to help determine risk trajectories is important for more effective treatment assignment. Secondary Aims: Data collected from actigraphy, saliva sample, and remote monitoring via the Beivei cellphone application will be used as preliminary evidence examining the effects of sleep-wake patterns, microbiome, and total physical activity on treatment outcomes in individuals experiencing depression.

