### **Accrual**

The MDD participants will be primarily recruited from the Outpatient Clinics of the University of Pennsylvania, including the Mood and Anxiety Disorders program, student health and the general adult psychiatry programs. These programs see 400+ new patients with depressive disorders each year and contributed 72 unmedicated MDD participants across 30 months to the recently completed noninferiority study of CCBT. Should the need arise, we also can recruit from the Philadelphia VA Medical Centers Behavioral Health Laboratory (PVAMC-BHL). As the BHL continuously screens from the primary care clinical population of the PVAMC, it will serve as a rich secondary recruitment resource for individuals for this study. As an example, from August 2013 to August 2014, 1,298 individuals between ages 18 and 45 completed assessments within the BHL. Of the 1,194 individuals who completed full assessments, approximately 29.4% screened positive for MDD, providing an ample participant base from which to recruit. We thus anticipate no difficulty enrolling depressed patients into this study. Up to 120 participants will be consented for participation; however we anticipate that approximately 10% will screen fail and another 10% will either drop out during the study or have unusable scanner data; therefore, we aim to have 60 participants with MDD and 40 healthy control participants who complete the entire study with usable data. C.10.1 Power Analysis For Aim 1, based on our pilot data, we assume that DLPFC in HC is positively correlated with amygdala with correlation of  $r=0.1$ , while in contrast it is negatively correlated in MDD with correlation  $r=-0.1$  (standard deviation 0.07). Similarly, our pilot data indicates that IFC in MDD is 70% less correlated with the amygdala than in HC (standard deviation 0.07). Given 60 MDD patients and 40 HC at baseline, we have excellent power (80%) to detect the differences between MDD and HC for their baseline amygdala connectivity in DLPFC and IFC. For subgroup analysis in subjects of each sex separately, we will also have 80% power to detect differences between MDD and HC. Similarly, for baseline task measures, the pilot data indicate up to two-fold higher activation in HC in the four targeted regions (ACC, DLPFC, IFC), indicating that will also have 80% power to detect such differences between MDD and HC (in males and females separately, as well as combining sexes) at the 95% confidence level adjusting for the number of tests. For Aim 2, based on our pilot data, the correlation between IFC and amygdala will increase by 0.09 after CCBT (standard deviation 0.05), and the correlation between precuneus and amygdala will decrease by 0.08 (standard deviation 0.04). We will have 80% power to identify treatment effects comparing the data from 30 MDD patients receiving CCBT in 1-2 weeks with untreated data from the subjects receiving CCBT in 3-4 weeks. We will also have 80% power to detect different treatment effects in males and females separately. For longitudinal changes in activation, we

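### The 80% power for baseline task activation is stated for four targeted regions, but Aim 1b specifies no region-level MDD versus control test, and its region list omits the rostral ACC

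*Combined protocol and SAP*

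**What the plan says.** Baseline emotional conflict task activation is a primary outcome (Primary outcome variable(s), Aim 1b). Four places bear on how it will be tested.

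- **Hypothesis** (Overall objectives, 1b): depressed participants will show "decreased emotional conflict task-induced activation in rostral/dorsal anterior cingulate cortex (ACC), dorsal lateral prefrontal cortex (DLPFC), and inferior frontal gyrus (IFG").
- **Power** (Accrual, C.10.1 Power Analysis): the effect assumed for baseline task measures is "up to two-fold higher activation in HC in the four targeted regions (ACC, DLPFC, IFC"). From that effect the section concludes that power for the MDD versus control comparison is 80%. It makes this claim for each sex separately and for the sexes combined, at 95% confidence after adjustment for the number of tests. The sample is given just before: "Given 60 MDD patients and 40 HC at baseline". Four regions are announced and three named. The Aim 2 power text that follows gives detectable changes for right IFC, left IFC, ACC and DLPFC, which is the natural source of the count of four.
- **Analysis** (Analysis Plan, C.10, Aim 1b): the target is "baseline differences between MDD and HC in Emotional Conflict task-induced activation in the dorsal ACC, DLPFC, and IFC". Two approaches are listed. The first is to "perform the voxel-wise general linear model to detect group differences on the AHIF-AHIN contrast". The second is a brain-wide fPCR that explores variation associated with depression symptoms, controlling for anxiety symptoms. Both are adjusted for age and sex, with false discovery rate (FDR) control.
- **Neighbouring aims**: regional averaging appears in Aim 1a, for amygdala connectivity and as a comparison method. Targeted mixed-effects modelling appears in Aim 2b, for change over treatment.

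**The concern.** A power statement is useful only if it belongs to the test that will decide the hypothesis. Four targeted regions with an adjustment for the number of tests describes a short, countable family of region-level comparisons. The only MDD versus control comparison specified for baseline task activation is a voxel-wise model with FDR control, and neither its search volume nor its threshold is stated. The fPCR approach is worded as exploratory and relates activation to symptoms rather than to group. The rostral ACC is in the hypothesis but is not a named target of the analysis.

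At stake is how a null result is read, because the plan gives no power for the group comparison it specifies. The choice of mask, ACC subregion or region average is also left open until after the data can be seen.

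**Working it through.** **1. Can the stated 80% be reproduced?** No. The section gives no mean or SD for task activation; the SD of 0.07 belongs to the connectivity correlations. A two-fold difference means that the group difference is half the control mean, so d = 0.5/CV, where CV = SD divided by the control mean. For 60 versus 40, with four tests at two-sided 0.05/4 = 0.0125 (sidedness and method are assumed), assumed CVs of 0.5, 0.75, 1.0 and 1.5 give power of 99%, 78%, 48% and 19%. The 80% is therefore neither confirmed nor refuted.

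**2. What effect does 80% imply?** Under the normal approximation the noncentrality is λ = z(1−α/2) + z(0.80), and d = λ × √(1/60 + 1/40) = λ × 0.204.

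- α = 0.05: λ = 1.960 + 0.842 = 2.80, d = 0.57.
- α = 0.0125: λ = 2.498 + 0.842 = 3.34, d = 0.68.

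**3. The per-sex claim.** The same sentence claims 80% within each sex. The sex split is not given; assume half the sample, 30 versus 20. If one effect has 80% power there, the full-sample noncentrality is larger by √2: 2.80 × 1.414 = 3.96, or 3.34 × 1.414 = 4.72.

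**4. Power at a stricter cut-off.** At one voxel with the same signal-to-noise, power is Φ(λ − z(1−t/2)), with z = 2.576, 3.291 and 3.891 at t = 0.01, 0.001 and 0.0001. These cut-offs are assumptions, because the one implied by FDR depends on the data.

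| Reading of the 80% | λ | p<0.01 | p<0.001 | p<0.0001 |
|---|---|---|---|---|
| Full sample, α = 0.05 | 2.80 | 59% | 31% | 14% |
| Full sample, α = 0.0125 | 3.34 | 78% | 52% | 29% |
| Each sex, α = 0.05 | 3.96 | 92% | 75% | 53% |
| Each sex, α = 0.0125 | 4.72 | 98% | 92% | 80% |

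For example, in the first row at p<0.001: Φ(2.80 − 3.29) = Φ(−0.49) = 31%.

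**5. Region lists side by side.**

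| Place | ACC | Other regions |
|---|---|---|
| Hypothesis 1b | rostral/dorsal | DLPFC, IFG |
| Power, baseline | ACC, no subregion | DLPFC, IFC (four stated) |
| Power, Aim 2 change | ACC, no subregion | DLPFC, right IFC, left IFC |
| Analysis, Aim 1b | dorsal only | DLPFC, IFC |

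**The case against.** Several points on the other side stand.

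- A reader might infer that the powered test will never be run. The documents do not show that. The Aim 1b sentence frames both approaches as assessing named regions, and only the fPCR is called brain-wide, so the voxel-wise model may be meant for those regions. What can be said is that no region-level test or restriction is specified. That the 80% refers to region averages is likewise an inference from the wording.
- A reader might take 14% as the power of the planned analysis. That is the least favourable corner of the table and ignores the per-sex claim. The figures are also for one pre-chosen voxel. A region counts as detected if any of its voxels survive, which is easier, and a focal voxel may carry a larger effect than a diluted region mean.
- A reader might cite the plan's remark that fPCR "has more power than voxel-wise searches" as the authors ranking region means above voxels. It does not. It concerns fPCR on connectivity maps, and Aim 1a also expects fPCR to be more sensitive than regional averaging. Demoting fPCR would be a preference, not a correction.
- The count of four is explained by the Aim 2 list, and IFG versus IFC looks like a naming variant. The power text says only ACC, so it makes no rostral claim that could be contradicted, and a brain-wide search still covers that region.

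None of this supplies the missing test. Regional averaging and targeted modelling are written into other aims, so the authors specify such analyses when they intend them.

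**Conclusion.** Wrong as written: the 80% is not attached to any test specified for hypothesis 1b. This rests on reading four targeted regions with a test-count adjustment as region-level tests, which is the natural reading but is not stated. The size of the power loss cannot be determined. Depending on what the 80% refers to and on the effective cut-off, single-voxel power lies anywhere from 14% to 98% under the assumptions shown, so the table illustrates that the figure does not transfer and does not estimate the trial's power.

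The rostral ACC point is narrower. A hypothesised region is not a named target of the Aim 1b analysis, which conflicts with hypothesis 1b but not with the power text. It would go too far to say that the region is left unexamined. It would also go too far to predict that a null voxel map will be reported as an 80%-powered null; the documents only leave room for that.

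**What to change.** - For hypothesis 1b, pre-specify a linear model of the mean AHIF-AHIN contrast on group, age and sex in each hypothesised region: rostral ACC, dorsal ACC, DLPFC, left IFG/IFC and right IFG/IFC. Apply Holm or FDR across the five.
- Keep the voxel-wise model and the fPCR alongside, and state whether the voxel-wise search is whole-brain or confined to a mask.
- Use one region list in the Overall objectives, the Primary outcome variable(s), the power section and Aim 1b.
- State that the 80% applies to the region-level tests only, and give the pilot means and SDs, the sidedness and the number of tests behind it.

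The cost is wording and five regressions on scans already planned. Five tests instead of four move a Bonferroni threshold from 0.0125 to 0.01. An effect with 80% power at 0.0125 then has Φ(3.34 − 2.576) = 78%, and Holm or FDR would lose no more than that. The form reports 4 subjects enrolled under this protocol, but data from protocol 826910 will be pooled, so the change should be fixed before group results are examined.
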